## 2.7 Sample size

The sample size calculation is based on the approach described by Hussey and Hughes. We specify a minimum clinically important difference of 15 percent in the number of patients readmitted to hospital within 90 days after baseline. Based on existing literature and expertise of the research team, we estimate a proportion of 35% readmissions at baseline. We use a conservative estimate of the intracluster correlation coefficient (ICC) of 0.05 and apply a correction for 30% drop-out, such as due to withdrawn consent.

Sample size calculations based on these assumptions yield 18 hospitals to be included and randomized across six countries, with three hospitals per country and an average of 17 patients recruited per wedge (68 patients total per hospital, 204 per country, 1224 patients in total). This gives at least 90% power to detect a difference of 15 percent at  $\alpha = 0.05$ .

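### The stated 90% power does not survive the stated 30% drop-out: 17 recruited per wedge leaves about 12 analysed and about 82% power

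*Protocol*

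**What the plan says.** Everything needed is in Protocol section 2.7, with the layout in sections 2.1 and 2.9.

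- Method: "The sample size calculation is based on the approach described by Hussey and Hughes".
- Control rate: "we estimate a proportion of 35% readmissions at baseline".
- Target effect: "We specify a minimum clinically important difference of 15 percent in the number of patients readmitted to hospital within 90 days after baseline".
- Clustering: a "conservative estimate of the intracluster correlation coefficient (ICC) of 0.05".
- Loss: the authors "apply a correction for 30% drop-out, such as due to withdrawn consent".
- Size: 18 hospitals, three from each of six countries. Recruitment is given as "an average of 17 patients recruited per wedge (68 patients total per hospital, 204 per country, 1224 patients in total").
- Claim: "This gives at least 90% power to detect a difference of 15 percent at" a significance level of 0.05.

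Sidedness is not stated, and neither is the variance convention. The number expected to be analysed is not given, only the number recruited.

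**The concern.** The total of 1224 equals 18 × 4 × 17, so both 17 and 1224 are recruitment figures. If 30% are lost, the loss comes out of those figures and about 12 patients per hospital per wedge remain. A design that only just exceeds 90% power with 17 per cell cannot keep that power with 12.

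Ethics committees in six countries and the trial's oversight bodies will rely on this figure. If power is really near 82%, the risk of a false negative on the primary outcome is close to twice what the protocol tells them.

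The wording of the effect is also loose. A difference of 15 percent could be read as relative (35% to 29.75%) or as percentage points (35% to 20%), and the two readings give very different power.

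**Working it through.** **Inputs**

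- Section 2.7: control rate 0.35; difference 0.15, read as percentage points, so 0.20 under intervention; ICC 0.05; alpha 0.05; drop-out 30%; 17 recruited per hospital per wedge; I = 18 hospitals.
- Section 2.1: T = 4 wedges; cross-over at 6, 12 or 18 months, so three sequences.
- Section 2.9: the three hospitals of each country are put in random order and cross over one at a time, so six hospitals per sequence.
- Assumed: two-sided test, normal reference.

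**Formula (Hussey and Hughes)**

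With X = 1 for an intervention cell, U = sum of X, W = sum over wedges of (wedge total)², V = sum over hospitals of (hospital total)², s² = within-hospital variance / n and τ² = between-hospital variance:

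Var = I·s²·(s² + T·τ²) / [(I·U − W)·s² + (U² + I·T·U − T·W − I·V)·τ²]

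- U = 6 × (3 + 2 + 1) = 36
- W = 0² + 6² + 12² + 18² = 504
- V = 6 × (9 + 4 + 1) = 84
- I·U − W = 648 − 504 = 144
- U² + I·T·U − T·W − I·V = 1296 + 2592 − 2016 − 1512 = 360

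Total variance at the mean rate is 0.275 × 0.725 = 0.199375. Then τ² = 0.05 × 0.199375 = 0.009969, and the within-hospital variance is 0.95 × 0.199375 = 0.189406.

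**The plan's figure: all 17 analysed**

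- s² = 0.189406 / 17 = 0.011142
- Var = 18 × 0.011142 × (0.011142 + 0.039875) / (144 × 0.011142 + 360 × 0.009969) = 0.010231 / 5.1931 = 0.001970
- SE = 0.0444
- Power = Φ(0.15 / 0.0444 − 1.96) = Φ(1.42) = 92.2%

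So the claim of at least 90% is reproduced, but with no loss at all.

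**With the stated loss: 17 × 0.7 = 11.9 analysed (1224 × 0.7 ≈ 857 in total)**

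- s² = 0.189406 / 11.9 = 0.015916
- Var = 18 × 0.015916 × (0.015916 + 0.039875) / (144 × 0.015916 + 3.58875) = 0.015984 / 5.8807 = 0.002718
- SE = 0.0521
- Power = Φ(0.15 / 0.0521 − 1.96) = Φ(0.92) = 82.0%

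**Sensitivity to the variance convention (two-sided 0.05)**

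| Variance used | 17 analysed | 11.9 analysed |
|---|---|---|
| Mean rate, total | 92.2% | 82.0% |
| Average of the two arms, total | 92.9% | 83.1% |
| Mean rate, within-hospital | 90.9% | 80.1% |
| Control rate, total | 88.6% | 76.8% |
| Control rate, within-hospital | 86.9% | 74.7% |
| 20% rate, within-hospital | 95.7% | 87.9% |
| 20% rate, total | 96.5% | 89.5% |

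No row reaches 90% at 11.9. Varying the ICC from 0.01 to 0.20 (mean rate) gives about 82% to 87%, and only an ICC close to 0 passes 90%.

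A simulation with a logistic mixed model (1000 runs per setting) agrees. With a normal reference, power was 93% at 17 and 85% at 12. With a t reference on 16 degrees of freedom it was 91.5% and 80%.

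**What the design can do (mean rate, total variance)**

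- Detectable difference at 90% power with about 12 analysed: (1.96 + 1.28) × 0.0521 = 0.169, about 17 points.
- 90% power needs 15.5 analysed, so the tolerable loss is 1 − 15.5/17, a little under 9%.
- 5% loss (16.15 analysed): 91.0%. 10% loss (15.3 analysed): 89.6%.

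**Relative reading of 15 percent**

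For 35% to 29.75% (5.25 points), power is about 20% at 17 and 16% at 11.9. Only percentage points can have been meant.

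**The case against.** **The primary outcome comes from records.** This is the strongest counter-argument. Section 2.10 takes readmission from the medical record and section 2.12 specifies intention-to-treat, so a missed questionnaire need not remove a patient. If only 5% were lost, power would be 91.0% and the claim would stand. But section 2.7 applies the 30% to the calculation for this very outcome and gives withdrawn consent as an example, which may also end access to records. Nothing there limits the 30% to questionnaires.

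**A one-sided test.** Section 2.6.2 states a directional hypothesis, and sidedness is not given. A one-sided 5% test at 11.9 analysed gives 87.7% to 89.9% under the mean-rate and averaged conventions. It reaches 90.1% with averaged variance if 11.9 is rounded up to 12, and about 94% if the variance is taken at the 20% rate. That comes close to the stated figure, but no one-sided test is declared. If one was intended, the section needs that statement.

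**The cause is not certain.** Power above 90% at 17 suggests the correction was left out of the recruitment figure. Another route also fits: with mean-rate within-hospital variance, 11.9 is the number for 80% power and 11.9 / 0.7 = 17.0. On that route the correction is included and the power level is misstated. The document does not show which happened. Either way, the drop-out, recruitment and power figures disagree.

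**17 as the analysed number.** Recruitment would then be 17 / 0.7 = 24.3 per wedge, about 1,749 in total, which contradicts the stated 1224.

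**Conclusion.** The concern holds. On the protocol's own inputs and a two-sided 5% test, 17 recruited with 30% lost gives about 82% power for 35% versus 20%. The range is about 75% to 83% under the common variance conventions, with 89.5% as the most favourable. The type II error is about 18% against the stated 10%, and the difference detectable with 90% power (about 17 points) is larger than the stated minimum clinically important difference.

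The conclusion assumes two-sided testing and that the 30% applies to the primary outcome. The first is the usual default; the second is how section 2.7 reads. The exact figure depends on a variance convention the protocol does not give, but the failure to reach 90% does not. This must be corrected, because the main power statement does not follow from the assumptions printed beside it.

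**What to change.** Rewrite the power statement in section 2.7 so that the figures agree, for example: *17 patients recruited and about 12 analysed per hospital per wedge (1224 recruited, about 857 analysed) give about 82% power at a two-sided 5% level for 35% versus 20%, a difference of 15 percentage points, or 90% power for a difference of about 17 percentage points.* Name the variance convention and show the loss step, so that a reader can reproduce the figure. If the sponsor's convention differs from the mean-rate total variance used here, its own figure should replace the 82%.

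If the 30% concerns questionnaires only, say so, state the loss expected for record-based readmission, and quote power at that loss (91.0% at 5%, 89.6% at 10%). If a one-sided test was intended, declare it.

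The cost is text only, with a less favourable power figure unless a lower loss is justified. No extra patients are requested. Should the sponsor prefer to keep 90% power with 30% loss, the mean-rate and averaged conventions need about 15.0 to 16.4 analysed. Dividing by 0.7 gives about 22 to 24 recruited per hospital per wedge, or 72 × 22 = 1584 to 72 × 24 = 1728 in total.

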## 2.8 Recruitment

In each country, three eligible hospitals are being recruited, with clinical teams engaged to participate in the study and carry out the intervention. Informed consent will be sought from clinicians for the data collection as part of the process evaluation.

Patients admitted to hospital with an exacerbation of COPD will be flagged by hospital staff. Eligible patients will be approached concerning study participation by a member of the respiratory team. With the patient's agreement, the patient's contact details are provided to the local researcher, who will invite eligible patients for informed consent to participate in the study.

Family caregivers will be identified through eligible patients. Permission will be sought from the patient to approach this person for participation. Patients may still participate even if they do not identify a family caregiver or if the family caregiver does not wish to participate.

Informed consent will be obtained from patients and caregivers after providing information about the purpose of the study and data collection, using the Information Sheet.

## 2.9 Randomization and allocation

Hospitals will be randomized as to when they cross over from the control condition to the intervention, centrally by UGENT. The full list of 3 hospitals for each country will be randomized at study onset. At 4, 10, and 16 months, the next hospital in the list (Hospital 1, Hospital 2, or Hospital 3) to cross over is unblinded.

## 2.9.1 Masking/blinding

Hospitals are randomized according to their number (1, 2, or 3) only. However, participants and researchers cannot be fully blinded, as the intervention differs from treatment as usual and there is a training period for clinicians preceding the implementation.

## 2.10 Data collection procedures

The **primary outcome** (percentage of participating patients readmitted to hospital within 90 days of baseline, or until death if within these 90 days) will be collected via routinely-collected data regarding hospitalization in the patient (electronic) medical record. A data retrieval form will be used to collect data from the patient health record.

Patients and family caregivers enrolled in the study will be asked to complete questionnaires for **secondary outcomes** at baseline (T0, immediately following informed consent), and at 30 and 90 days post-baseline. If a patient dies during the trial, caregivers who consented will be contacted 3 months post-bereavement to complete the VOICES-SF questionnaire. Additional data regarding healthcare utilisation of enrolled patients will be collected through medical notes, consulting the patient's ICLEAR-EU form, and consulting with the general practitioner (GP) or other home/community care when possible and appropriate.

Data for the **cost-effectiveness evaluation** includes the CSRI and EuroQol (EQ-5D-5L) at 30 and 90 days, alongside other trial data collection through the participant interview. Unit costs will be identified first by literature search and, where necessary, by calculation by the research team. The economic evaluation will also utilize the hospital data to model intensity of hospital stay for a given patient profile.

For the **process evaluation**, both quantitative and qualitative data addressing the PRISM/RE-AIM domains will be collected throughout the study (see Table 3 for timing). Quantitative data will be collected using structured checklists, questionnaires, monitoring recruitment numbers, and short surveys; these will be conducted at set time points at the trial timeline and intervention timeline level, including pre-and post-training, after ICLEAR-EU meetings, and at the end of a wedge. Data will be collected via ICLEAR-EU team members attending the trainings and ICLEAR-EU meetings, and from the coordinator and/or clinical champion.

Semi-structured interviews for qualitative data collection will be conducted as follows:

- Per hospital: During the intervention phase, two patients will be selected by convenience sampling from the participants, to be interviewed approximately 4 weeks after discharge from hospital about their experiences with received care; although an individual interview is recommended, the patient can also opt for an interview with his/her relative present.
- Per hospital: During the intervention phase, 2 bereaved family caregivers will be selected by convenience sampling from the participants and invited to share their experiences with the care received, three months after bereavement .
- Per hospital: two clinicians (clinical coordinator and/or champion) will be interviewed about their experiences with the intervention and suggestions for maintenance after the last intervention wedge

## 2.11 Data management

Data collected during the project will be entered into REDCap, an internationally recognized system for data management and recording for clinical trials. The Vrije Universiteit Brussel takes overall responsibility for data management throughout the project. A data management plan has been created and will be kept up to date throughout the course of the project, and a joint controller agreement will be in place to allow for transfer of data for analysis within the consortium.

The consortium additionally certifies that all research activities will adhere most strictly to all applicable legal, ethical and safety provisions of the individual states and of the EU. Participants will conform to relevant EU legislation including (1) The Charter of Fundamental Rights of the EU, December 2009 and (2) EU Regulation 2016/679 on the protection of natural persons with regard to the processing of personal data and on the free movement of such data (GDPR).

## 2.12 Statistical methods

A statistical analysis plan (SAP) will be developed to prespecify and guide analyses in this trial (Work Package 7 D7.1). All analyses will follow intention-to-treat (ITT). Participants will be assessed according to whether they entered the study during a control wedge or an intervention wedge.

### 2.12.1 Primary outcome

To determine the effectiveness of the ICLEAR-EU intervention, we will compare the primary outcome between control and intervention participants using a logistic mixed model approach. The model will include a random effect for the cluster, and fixed effects for the condition (control or intervention), country, and time. A fixed effect interaction between condition and time will capture whether effects change over time. A fixed-effect interaction term between country and time will be added to allow for varying secular trends between countries. Gender will be added as a covariate in the analysis, as it has been shown to relate to outcomes in COPD.

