## 1 Introduction

People with chronic obstructive pulmonary disease (COPD) experience significant symptom burden, leading to declining functional status and frequent hospitalizations in the advanced stages of the disease. This population often experiences unmet needs, including physical, emotional, social, and existential care needs. Exacerbations and hospitalisations for COPD are a risk factor for subsequent readmission; data collected from COPD admissions in 13 European countries shows that 35% of patients discharged for an exacerbation were readmitted within 90 days. This leaves patients vulnerable to rapid health deterioration after the first exacerbation and admission to hospital. Palliative care can improve the quality of life for patients with COPD by addressing needs across physical, psychological, social, or spiritual domains. However, people with COPD are an underserved population in this regard: although the palliative care needs of people with COPD could be as high as those of people with (lung) cancer, referral and access to (specialist) palliative care are limited in comparison.

A proactive approach to palliative care is needed, which integrates palliative care into routine care for COPD. Integrated palliative care actively involves the patient, family, and multidisciplinary clinical teams who are trained in the palliative care approach, ensuring continuity between all services involved. Early integration of palliative care is essential to reducing potentially preventable readmissions for patients with COPD.

The EU PAL-COPD project aims to achieve better quality of life and improved well-being for people with advanced COPD, by integrating palliative care into respiratory care via an innovative, non-pharmacological service-based intervention called ICLEAR-EU. The ICLEAR-EU intervention focuses on early identification of palliative care needs, multidisciplinary care integration including palliative, respiratory, and primary/community care, shared decision-making and advance care planning, and ongoing review of patient needs. The intervention is based on a model introduced in the United Kingdom (UK), where this multidisciplinary approach resulted in a reduction in hospital deaths.

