#### \*Advanced COPD

1. Spirometry (FEV1):
  - a. Severe COPD:  $30\% \leq \text{FEV1} < 50\%$  predicted **OR**
  - b. Very severe COPD:  $\text{FEV1} < 30\%$  predicted

OR

2. High symptom burden:
  - a. Modified Medical Research Council (mMRC)  $> 2$  **OR**
  - b. COPD Assessment Test (CAT)  $> 20$

OR

3. High-risk exacerbation history:
  - a.  $\geq 1$  exacerbation leading to previous hospitalisation in the past year **OR**
  - b.  $\geq 1$  exacerbation leading to previous ICU admission in the past year

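### The primary model's single hospital intercept can understate the standard error if within-hospital correlation decays between wedges; adding a hospital-by-wedge effect, and age beside gender, is cheap protection.

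*Protocol*

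**What the plan says.** Protocol section 2.12.1 specifies a logistic mixed model: "The model will include a random effect for the cluster, and fixed effects for the condition (control or intervention), country, and time". It adds a condition-by-time interaction and a country-by-time interaction: "A fixed-effect interaction term between country and time will be added to allow for varying secular trends between countries". The only patient-level covariate is gender: "Gender will be added as a covariate in the analysis, as it has been shown to relate to outcomes in COPD". No hospital-by-wedge random effect appears. Section 2.12.2 does name a further random effect where one is wanted, for repeated measurements within patients.

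Section 2.7 sizes the trial by the Hussey and Hughes approach: "We use a conservative estimate of the intracluster correlation coefficient (ICC) of 0.05", and "18 hospitals to be included and randomized across six countries, with three hospitals per country and an average of 17 patients recruited per wedge". It gives no ratio of between-wedge to within-wedge correlation. Section 2.1 sets four six-month wedges, with cross-over at 6, 12 or 18 months.

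On case mix, the Introduction states: "Exacerbations and hospitalisations for COPD are a risk factor for subsequent readmission". The definition of advanced COPD in section 2.3 includes, as one of several alternative routes, at least one "exacerbation leading to previous hospitalisation in the past year". Table 2 collects age at T0. Under section 2.8 hospital staff flag patients and the respiratory team approaches them; section 2.9.1 accepts that full blinding is not possible. Section 2.12 leaves further detail to a SAP.

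**The concern.** A single intercept treats a hospital's level as fixed for two years apart from the fixed time effects. The protocol gives some reason to doubt this. Control care follows each hospital's own routine (section 2.5.1), and current practice is surveyed again at the end of every wedge (section 2.6.5), which makes most sense if practice can change.

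The country-by-time term removes only shifts shared by a country's three hospitals. All hospitals are in control in the first wedge and all are in intervention in the last. The concurrent comparison within a country therefore rests on the two middle wedges, one hospital against two. Drift of a single hospital is noise in exactly that comparison. If it exists and the model has no term for it, the confidence interval is too narrow and the primary test too liberal.

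The second issue is separate. Eligibility involves a judgement about who may benefit from integrated palliative care, made by staff who know the hospital's condition. Case mix may therefore shift at cross-over, and gender alone gives little protection against that.

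**Working it through.** **Inputs.** From the protocol: I = 18 hospitals (three per country, one per cross-over time), T = 4 wedges, 17 recruited per wedge, 35% readmitted, a difference of 15 (read as percentage points, so 20%), ICC 0.05, 30% drop-out, alpha 0.05 (taken as two-sided). Assumed: a between-wedge to within-wedge correlation ratio r of 1, 0.8 or 0.5. Patients analysed per wedge, m: 17, or 12 after drop-out (17 × 0.70 = 11.9).

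**Formula.** On wedge means, with t² the hospital variance and s² the variance of a wedge mean around its hospital's level:

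Var = I·s²·(s² + T·t²) / [(I·U − W)·s² + (U² + I·T·U − T·W − I·V)·t²]

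Here U = 6 × (3+2+1) = 36, W = 0² + 6² + 12² + 18² = 504 and V = 6 × (9+4+1) = 84. The bracket becomes 144·s² + 360·t².

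**Step 1: the plan's own figure.** Mean proportion 0.275; total variance 0.275 × 0.725 = 0.199375; t² = 0.05 × 0.199375 = 0.00997; patient variance 0.18941; s² = 0.18941/17 = 0.01114.

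Var = 18 × 0.01114 × (0.01114 + 0.03988) / (1.604 + 3.589) = 0.00197, so SE = 0.0444. Power = Φ(0.15/0.0444 − 1.96) = 92%. The stated power of at least 90% is reproduced with 17 analysed. With 12 analysed, SE = 0.0519 and power is 82%.

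**Step 2: add decay.** A hospital-by-wedge effect takes the share (1 − r) of the hospital variance, so t² becomes r × 0.00997 and s² gains (1 − r) × 0.00997. For m = 17 and r = 0.8: s² = 0.01114 + 0.00199 = 0.01314 and t² = 0.00798. Then Var = 18 × 0.01314 × (0.01314 + 0.03190) / (1.891 + 2.871) = 0.00224, so SE = 0.0473.

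**Step 3: what the single-intercept model reports.** Fitted to such data by maximum likelihood, it settles in large samples on a hospital variance of 0.0085 and a patient variance of 0.1909 (m = 17, r = 0.8). In the formula these give a reported SE of 0.0442. The actual SE of its estimate, by the sandwich formula, is 0.0473. Type I error = 2Φ(−1.96 × reported/actual).

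| Analysed per wedge | r | Reported SE | Actual SE | Reported/actual | Type I error |
|---|---|---|---|---|---|
| 17 | 1 | 0.0444 | 0.0444 | 1.00 | 5.0% |
| 17 | 0.8 | 0.0442 | 0.0473 | 0.93 | 6.7% |
| 17 | 0.5 | 0.0437 | 0.0508 | 0.86 | 9.2% |
| 12 | 1 | 0.0519 | 0.0519 | 1.00 | 5.0% |
| 12 | 0.8 | 0.0517 | 0.0541 | 0.95 | 6.1% |
| 12 | 0.5 | 0.0510 | 0.0567 | 0.90 | 7.8% |

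The ratios do not depend on the total variance chosen. A slightly different approximation of the fitted variances moves the worst case to 0.85 and 9.7%.

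**Step 4: country-by-time.** Within one country I = 3, U = 6, W = 14 and V = 14, so the bracket is 4·s² + 10·t² and the numerator has 3 in place of 18. That variance is exactly six times the one above. Averaging six countries returns the same value, so the term leaves every figure in the table unchanged.

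**Limits.** This is a linear approximation to a logistic model, with a normal reference, and it leaves out condition-by-time and gender.

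**The case against.** The strongest reply is that the harm is conditional. A reader might infer that the standard errors are too small and that the false-positive rate exceeds 5%. The protocol does not support that: it neither states nor implies a decay ratio, and at r = 1 reported and actual SE agree. This stands, and the conclusion is worded accordingly.

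Second, simulation does not isolate the intercept cleanly. A logistic model with country-by-wedge effects, a hospital intercept and a z-test rejected in 7.2-7.9% of null trials with no drift, against 7.9-8.4% at a ratio of 0.8 (Monte Carlo error 0.6-0.8 points). A smaller independent set with country-by-time gave 8.3-10.0% with no clear trend in the ratio (Monte Carlo error about 1.2 points). Much of that excess comes from using a z-test with 18 hospitals. The protocol names no reference distribution, so the z-test is a software default and the SAP may settle it; it is no fault of this document. What remains is that a better reference does not cure the missing term: with a t reference on 16 degrees of freedom the simulated rate was about 5% without drift but 6.3-7.4% with it.

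Third, a reader might link the covariates to the standard errors, or assume that prior-year hospitalisation is on file for everyone. Omitting a covariate costs precision and protection against imbalance; it does not make standard errors too small. The routes to advanced COPD are alternatives, so a patient who qualifies on spirometry need not have an exacerbation history recorded, and Table 2 does not list it. The Introduction's risk-factor statement is also general: every enrolled patient has just been admitted for an exacerbation, and it does not single out the past year. Nor does the protocol say that age predicts readmission; the case for age is that it is already collected.

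**Conclusion.** The concern holds in conditional form. Section 2.12.1 fixes a random-effects structure that is right only if within-hospital correlation stays constant over 24 months. If it decays, the standard error of the condition effect is understated by about 5-7% at a ratio of 0.8 and 10-14% at 0.5, and two-sided type I error can rise to about 6-7% or 8-9%. These figures rest on ICC 0.05, 12 to 17 analysed per wedge, assumed ratios and a linear approximation. Country-by-time gives no protection, and with no decay there is no error.

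The covariate point is a separate and smaller improvement. It answers the risk of case-mix shift under unblinded recruitment and has no bearing on the standard-error figures.

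**What to change.** In section 2.12.1, add a hospital-by-wedge random effect beside the hospital intercept. Have the SAP pair it with a small-sample reference distribution or a permutation test of the cross-over order, suited to 18 hospitals. The operating characteristics of that combination have not been simulated here and should be checked when the SAP is written.

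Add age, already collected at T0, as a fixed covariate with gender. Add hospitalisation for exacerbation in the past year (yes/no) if it is recorded for every patient; this may need one extra item on the record-retrieval form described in section 2.10.

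The cost is wider confidence intervals if there is decay. By the formula above, power for 15 points at a ratio of 0.8 is Φ(0.15/0.0473 − 1.96), about 89%, with 17 analysed per wedge, and about 79% with 12. With no decay the figures are 92% and 82%. The loss reflects uncertainty that the single-intercept model would hide.

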## **2 Methods**

### **2.1 Trial design**

We have chosen a stepped wedge cluster-randomized controlled trial design for this study, which is a pragmatic design that allows every participating hospital the opportunity to receive the intervention.

The stepped wedge cluster-randomized controlled trial will proceed in a similar fashion across the six countries (Belgium, the Netherlands, the United Kingdom, Denmark, Hungary, and Portugal). Clustering is at the level of hospital sites. Each country will include three hospitals. A schematic representation of the trial design is shown in Figure 1.

[figure not shown]

Figure 1. Stepped wedge design of the trial

Each hospital will go through four wedges, each wedge with a duration of six months, for a total of 24 months. Each hospital starts in control condition and crosses over to the intervention condition at 6, 12 or 18 months. The timing of cross-over will be randomly assigned at study onset. Before a hospital crosses over from the control condition to the intervention condition, a 30-day transition period will be integrated into the last control wedge, during which clinicians will receive the intervention training and implementation support will be provided.

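### The primary model includes a condition-by-time interaction but names no primary contrast, so its condition coefficient depends on how time is coded and need not be the constant effect that was powered

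*Protocol*

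**What the plan says.** Section 2.12.1 describes a logistic mixed model for 90-day readmission: "The model will include a random effect for the cluster, and fixed effects for the condition (control or intervention), country, and time". It then adds two interactions. The first is "A fixed effect interaction between condition and time will capture whether effects change over time". The second is "A fixed-effect interaction term between country and time will be added to allow for varying secular trends between countries". Neither is labelled secondary, exploratory or a sensitivity analysis. The section does not say whether time is categorical or linear, or calendar time or time since cross-over, and it names no coefficient or contrast as the primary effect.

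On the design, section 2.1 says "Each hospital will go through four wedges, each wedge with a duration of six months, for a total of 24 months" and "Each hospital starts in control condition and crosses over to the intervention condition at 6, 12 or 18 months". It also says "Each country will include three hospitals", which with three cross-over times gives one hospital per sequence per country.

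On power, section 2.7 says "The sample size calculation is based on the approach described by Hussey and Hughes" and "We specify a minimum clinically important difference of 15 percent in the number of patients readmitted to hospital within 90 days after baseline". In its standard form that approach has categorical periods, a random cluster effect and one constant intervention effect, with no interaction.

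**The concern.** Once an interaction with time is in the model, the condition coefficient is no longer the overall effect. It is the effect at whichever wedge or time origin the coding happens to choose. This design makes the problem sharper, because two of the four wedges contain no within-wedge comparison of intervention with control.

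At stake is the trial's only primary hypothesis test. If the analyst fits the model as written and reports the condition row of the output, the test may have much less power than section 2.7 claims. If the contrast is chosen later, the choice could be made with the results in view. Section 2.12.2 carries similar modelling over to the secondary outcomes, so the ambiguity spreads to them.

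**Working it through.** **Inputs (protocol 2.1 and 2.7).** 18 hospitals; 4 wedges; 3 sequences of 6 hospitals; ICC 0.05; readmission 35% against 20%, reading the 15 percent as absolute; 17 recruited per hospital-wedge; 30% drop-out. Section 2.7 does not make clear whether 17 is before or after drop-out, so both 17 and 17 × 0.7 = 11.9 analysed are shown. Alpha is 0.05, taken as two-sided. Powers use a linear approximation on the risk-difference scale.

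**Step 1: reproduce the plan's power.** Mean proportion 0.275, so total variance is 0.275 × 0.725 = 0.1994. Between-hospital variance is τ² = 0.05 × 0.1994 = 0.00997. Cell-mean variance is s = 0.95 × 0.1994 / 17 = 0.01114.

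The numbers of intervention hospitals in wedges 1 to 4 are 0, 6, 12 and 18. So U = 36 and W = 6² + 12² + 18² = 504. Hospitals have 3, 2 or 1 intervention wedges, so V = 6 × (9 + 4 + 1) = 84.

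Hussey-Hughes variance = I·s·(s + Tτ²) / [(IU − W)s + (U² + ITU − TW − IV)τ²], with I = 18 and T = 4:
- IU − W = 648 − 504 = 144
- U² + ITU − TW − IV = 1296 + 2592 − 2016 − 1512 = 360
- Variance = 0.01023 / 5.193 = 0.00197, so SE = 0.0444
- Power = Φ(0.15/0.0444 − 1.96) = 92.2%

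With 11.9 analysed, SE is 0.0521 and power 82%. The stated figure of at least 90% is therefore reproduced for one constant effect with 17 analysed per hospital-wedge. Generalised least squares on the 72 hospital-wedge cells gives the same SE with and without country-by-time terms.

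**Step 2: categorical calendar wedge with the interaction.** The columns are 24 country-by-wedge cells, condition and three condition-by-wedge terms, 28 in all. The rank is 26 (11 of 13 without country-by-time). One column is lost because wedge 1 has no intervention data, so the condition main effect is the sum of the three interaction columns. The other is lost because the wedge-4 interaction column coincides with the wedge-4 time effect. The wedge-2 and wedge-3 effects are estimable; the wedge-4 effect and the average over wedges 2 to 4 are not.

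| Contrast | SE (17) | Power (17) | SE (11.9) | Power (11.9) |
|---|---|---|---|---|
| Constant effect, no interaction | 0.0444 | 92% | 0.0521 | 82% |
| Wedge 2 alone, or wedge 3 alone | 0.0593 | 72% | 0.0700 | 57% |
| Average of wedges 2 and 3 | 0.0444 | 92% | 0.0521 | 82% |

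The first and third rows agree because, with categorical time, the constant-effect estimator weights the calendar-wedge effects 0.5, 0.5 and 0 for wedges 2, 3 and 4.

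**Step 3: time linear throughout.** All terms can be fitted. The condition coefficient is the effect at time zero. With 17 analysed per cell:
- wedges coded 0 to 3: SE 0.067, power 61% (47% with 11.9)
- wedges coded 1 to 4: SE 0.095, power 35%
- centred at mid-trial: SE 0.0444, power 92%

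The fitted model is the same each time; only the labelled row changes.

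**Step 4: time since cross-over.** All terms can be fitted. With 17 analysed, power is 90% for the first exposure wedge, 64% for the second, 37% for the third and about 68% for their average.

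**The case against.** The strongest reply has three parts.

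First, the section can be read as a main model followed by a separate question about heterogeneity. Section 2.12.2 uses the same construction for condition by country, where the purpose is plainly subgroup comparison. That reading is possible, but nothing in section 2.12.1 marks the term as supplementary, and the country-by-time term that follows it is clearly meant for the primary model.

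Second, section 2.12 announces a statistical analysis plan, which may settle the coding of time and the contrast. Those details alone would be no finding. But the protocol itself already places the interaction in the primary model. A later plan could name a contrast, but it could not make the wedge-4 effect estimable under categorical time, nor drop the term without departing from the protocol.

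Third, the interaction need not cost power. This stands in full: Step 2 shows a contrast within the interaction model that has exactly the powered precision, and so does centring linear time. A reader might infer that the model gives no usable treatment effect, that every contrast from it is far less precise, or that the interaction cannot be estimated at all. The documents support none of these. Aliasing arises only if time is the categorical calendar wedge, which section 2.12.1 does not state. What remains is that the protocol does not say which contrast is meant.

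**Conclusion.** The concern holds in a limited form. Section 2.12.1 fixes a condition-by-time interaction in the primary model without naming the primary contrast, while section 2.7 powers a single constant effect. Under calendar-time coding, whether categorical or linear, the condition coefficient depends on parameterisation; under time since cross-over a contrast must still be chosen. With 17 analysed per hospital-wedge, the nominal test has 72% power as a single-wedge effect under categorical time, and 35% to 92% under linear time, against 92% for the powered contrast.

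These figures assume an absolute 15-point difference, ICC 0.05, two-sided alpha 0.05, equal cell sizes and a linear approximation to the logistic model. In the logistic model the equality between the constant effect and the wedge-2/wedge-3 average will be approximate. The rank result depends on categorical calendar time, not on the variance assumptions. The defect is one of specification and is fully curable before analysis, but it concerns the sole primary test and should be corrected.

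**What to change.** State in section 2.12.1 that the primary test is the condition coefficient from the model without the condition-by-time interaction, and that time enters as the categorical calendar wedge. This is the model that was powered. Keep country-by-time, which leaves the SE unchanged in this balanced design. Move change of effect over time to a secondary analysis, preferably by wedges since cross-over, and carry the same wording into the statistical analysis plan.

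The cost is one sentence in the protocol and matching text in the analysis plan; conduct, sample and data collection do not change. One downside should be stated openly. If the effect varies with time since cross-over, the constant-effect estimate is not a plain average: its weights on the first, second and third exposure wedge are about 1.06, 0.15 and −0.21 (17 analysed), so a larger late benefit would pull the estimate down. The exposure-averaged effect should therefore be reported as a sensitivity estimate, with the note that its power is only about 68%.
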